# 9.1.1 **Primary endpoint(s)**

The term "adherence" as used in this protocol is used as an umbrella term capturing various aspects of how patients follow their treatment regimen, including "compliance", "persistence", and "overall adherence". Hence, the primary endpoints will be the following:

The primary endpoint is:

• Compliance to therapy (%)

Co-primary endpoints are:

- Persistence of therapy (yes, no)
- Overall adherence to therapy (yes, no)

# 9.1.2 Secondary endpoint(s)

The secondary endpoints are:

- Satisfaction with the BETACONNECTTM autoinjector
- Injection site pain
- Flu-like symptoms

- Analgesic use prior to Betaferon® application
- Intake of vitamin D, other vitamins, and nutrients
- Depression
- health related quality of life
- coping mechanisms\*
- self-management mechanisms
- social support\*
- fatigue
- cognition
- number of relapses at 12 and 24 months
- EDSS change at 12 and 24 months
- utilities of treatment

\*to be evaluated only in the subgroup of patients participating in the PTMS program.

#### 9.1.3 Strengths of study design

This is a prospective, non-interventional, multi-center, single arm cohort study with patients with relapsing remitting multiple sclerosis (RRMS) or patients with a clinically isolated syndrome (CIS) who are treated with Betaferon® or will be treated with Betaferon® and are willing to use the BETACONNECTTM autoinjector a routine clinical practice setting. This study will include patients from a more diversified and less selected patient population than in a clinical trial setting, using fewer eligibility criteria to be as representative as possible.

#### 9.2 Setting

The study will be conducted in in private neurological offices/clinics and neurology departments across Germany specialized in the treatment of MS patients. For each patient, the investigator will document data in standardized electronic case report forms (eCRF) at initial, follow-up and the final visit. It is planned to collect data from 250 patients with relapsing remitting multiple sclerosis (RRMS) or patients with a clinically isolated syndrome (CIS) who are treated with Betaferon® or will be treated with Betaferon® and are willing to use the BETACONNECTTM autoinjector in order to determine baseline predictors of adherence to Betaferon® treatment after 12 and 24 months. The decision upon treatment with Betaferon® is made at the discretion of the attending physician, according to his/her medical practice.

# 9.2.1 Eligibility

The study population will consist of male & female patients with relapsing remitting multiple sclerosis (RRMS) or patients with a clinically isolated syndrome (CIS) who are treated with Betaferon® or will be treated with Betaferon® and are willing to use the BETACONNECTTM autoinjector according to the attending physician's decision.

# 9.2.2 Inclusion criterion/criteria

- Patients aged ≥ 18 years with the diagnosis of relapsing remitting multiple sclerosis or a clinically isolated syndrome.
- Patients must be on treatment with Betaferon® or the decision to treat patients with Betaferon® has been made by the attending physician.
- Patients must be using or willing to use the BETACONNECTTM autoinjector for Betaferon® application.
- Written informed consent must be obtained.

#### 9.2.3 Exclusion criterion/criteria

- Patients receiving any other disease modifying drug.
- Contraindications of Betaferon® described in the Summary of Product Characteristics.
- Patients participating in any other clinical or non-interventional study, evaluating MS therapy.

#### 9.2.4 Withdrawal

Each patient has the right to refuse further participation in the study at any time and without providing any reason. A patient's participation is to be terminated immediately upon his/her request. In this non-interventional study, withdrawal from the study is independent of the underlying treatment. On the other hand, premature discontinuation of treatment, which includes switching from Betaferon® to other treatments, automatically implies end of documentation. While fully respecting the patient's rights, the investigator should seek to obtain the reason and record this on the Case Report Form (CRF).

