#### 8.2 Secondary objective(s)

Secondary objectives are to evaluate at each visit:

- Satisfaction with the BETACONNECTTM autoinjector,
- Injection site pain,
- Flu-like symptoms following Betaferon® application,
- Analgesic use prior to Betaferon® application,
- Intake of vitamin D, other vitamins, and nutrients,
- If adherence to Betaferon® treatment is associated with:
  - depression,
  - health related quality of life,
  - coping mechanisms\*,
  - self-management mechanisms,
  - social support\*,

- fatigue, and
- cognition.
- If adherence to Betaferon® treatment at 12 (24) months is associated with number of relapses at 12 (24) months.
- If adherence to Betaferon® treatment at 12 (24) months is associated with EDSS change at 12 (24) months.
- If adherence to Betaferon® treatment is associated with utilities of treatment (only baseline and final visit).
- With respect to the subgroup of patients participating in the PTMS program (participants from PTMS centers vs. participants from non-PTMS centers):
  - At each visit, if the PTMS program is associated with:
    - treatment adherence,
    - depression,
    - quality of life,
    - self-management mechanisms,
    - fatigue,
    - cognition.
- In the subgroup of patients participating in the PTMS program:
  - At each visit evaluation of:
    - social support,
    - coping behavior.

\*only for patients participating in the PTMS program.

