## **Final Visit and End of Observation period**

The final data collection (last visit) is after approximately 24 months, at discontinuation of therapy or at end of study (whatever is earlier). At this final observation point, the patient's condition and a treatment assessment will be documented, including:

- Date of follow-up visit (DD/MM/YYYY)
- Study continued (yes/no), if no
  - please complete end of observation visit
- Smoking (current, past, never)
- Employment status (employed, retired, keeping house, student, seeking work, self-employed, other, not reported)
- Marital status (married/partnership, single)
- Medical history
  - Concomitant diseases
  - Concomitant medication
    - Trade name or INN
    - Start date (at least year)
    - Stop date or "continued"
    - Daily dose, if applicable
    - Indication
- Disease course
  - Number of further demyelinating events/relapses (enter 0 if no further event since last visit)
    - If number >0: date of onset (DD/MM/YYY)/ongoing
- Specific MS history
  - BETACONNECTTM auto-injector device still used (yes/no)
    - If no, please tick: Betaferon® treatment (ongoing/prematurely discontinued/unknown)
    - If ongoing, please specify which way of injection is used
      - Manual injection, BETACOMFORT®, BETAJECT Comfort®, BETAJECT lite®, other
    - if prematurely discontinued
      - last date of Betaferon® injection (DD/MM/YYYY)

- reason [adverse event (please complete AE page), lack of efficacy, pregnancy, patient's wish, choice of other treatment (please specify)]
- Treatment days with Betaferon® since last visit
  - Number of expected treatment days
  - Number of true treatment days
- Local skin reactions (yes/no)
  - If yes; please tick
    - a) (redness, other discoloration, hematoma, induration, lipodystrophy/atrophy, necrosis)
    - b) (mild, moderate, severe)
- Participation in the BETAPLUS® nurse support program (yes/no; if no, please specify termination date)
- Participation in the PTMS program (yes/no; if no, please specify termination date)
- Intake of vitamin D supplements (yes vs. no; if yes which dosage?)
- Intake of other nutrients or vitamins (yes vs. no)
- EDSS
- Patient QQ results available (yes/no), if yes
  - please send back
- SF-36 results available (yes/no), if yes
  - please send back
- EQ-5D results available (yes/no), if yes
  - please send back
- CES-D results available (yes/no), if yes

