# 9.3.1 Variables to determine the primary endpoint(s)

The variables for our primary objective are:

- Compliance to therapy
- Persistence of therapy
- Overall Adherence to therapy

They will be derived in the following way:

Adherence to therapy:

In the medical literature there is no commonly agreed upon definition of adherence. The term adherence has largely replaced the term compliance, as it implies a less directive way of treatment, but acknowledges the patient's participation in the treatment plan in the sense of a shared-decision-making. Beyond this difference in definition both terms refer to the same aspect of treatment, specifically to what extend patient treatment behaviors match the treatment plan. Adherence may be measured in various ways. For our study we will ascertain adherence in different ways to account for different aspects of patient treatment behavior:

- Compliance in percentage—this measure allows a general appreciation of the average patient treatment behavior (and spread) in the whole cohort investigated. It will be calculated as follows:
   Compliance (%) = ((expected # of treatment days during observation period missed # of treatment days during observation period)/(expected # of treatment days during observation period))\*100
- 2. Persistence (dichotomous, yes vs. no)—this measure allows a special view on those patients that completely stopped taking their medication vs. those continuing ("persisting") their medication (regardless of the frequency of intake)
- 3. Overall adherence—this measure will combine compliance and persistence to account for and allow comparison with studies basing their analysis on the "medication possession ratio" (MPR). Patients will be defined as being adherent to therapy if they fulfill the following criteria:
  - a. They have been at least 80% compliant, i.e. injected  $\geq$ 80% of the expected Betaferon® dosages and
  - b. They have not dropped out of the study prior to the time of evaluation (i.e. they did not stop Betaferon® treatment for any reason including switching to another medication prior to the time of evaluation).

Based on this definition adherence will be a dichotomous variable, which can be either "yes" or "no".

4. Number of dosages missed - to further characterize and quantify non-compliance we will also calculate the number of dosages missed

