## 9.7 Data analysis

#### 9.7.1 Statistical considerations

Statistical analyses will be of explorative and descriptive nature. P-values <0.05 will be considered as statistically significant unless stated otherwise.

All variables will be analyzed descriptively with appropriate statistical methods: categorical variables by frequency tables (absolute and relative frequencies) and continuous variables by sample statistics (i.e. mean, standard deviation, minimum, median, quartiles and maximum). Continuous variables will be described by absolute value and as change from baseline per analysis time point, if applicable.

All analyses will be performed for the total study population (overall analysis) or when defined otherwise within a valid subpopulation. Patients receiving at least one dose of Betaferon® will be included in the analysis. Whenever reasonable, data will be stratified by subgroups (e.g. age, gender, baseline characteristics).

There will be no further documentation of patients fulfilling the following criteria (end of observation visit will be documented): 1. patients terminating Betaferon® treatment including those stopping treatment overall or switching to other treatments; 2. patients lost to follow-up; and 3. patients choosing to terminate study participation for any reason. During the final visit (in case of premature termination) the investigator should try to identify the date, when Betaferon® treatment was discontinued. If this date cannot be identified or approximated, e.g. if a patient is lost to follow-up, the date of the last documented visit should be chosen. Further, the investigator should make every effort to identify the reason, why a patient decides to terminate the study. Reasons for study termination will be displayed using descriptive statistics.

All therapies documented will be coded using the World Health Organization – Drug Dictionary (WHO-DD). Medical history, any diseases and AEs will be coded using the latest Medical Dictionary for Regulatory Activities (MedDRA) version.

All statistical details including calculated variables and proposed format and content of tables will be detailed in the Statistical Analysis Plan (SAP). The SAP will be finalized before study database lock. The SAP is available upon request (see BF1502\_SAP\_final\_yyyymmdd Table 2: List of stand-alone documents, Annex 1).

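### Documentation ends when Betaferon stops, so in non-persistent patients the 12/24-month relapse count is truncated and the 12/24-month EDSS change is unobserved

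*Protocol*

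**What the plan says.** Three places in the protocol end data collection with treatment:

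- Section 9.2.4: stopping Betaferon early, a term that covers switches "to other treatments, automatically implies end of documentation".
- Section 9.2.7, in its part on the last visit, sets the timing: "The final data collection (last visit) is after approximately 24 months, at discontinuation of therapy or at end of study (whatever is earlier").
- Section 9.7.1: "There will be no further documentation of patients fulfilling the following criteria", the first criterion being termination of Betaferon or a switch. Only an end-of-observation visit remains.

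Section 9.3.1 builds the same event into the grouping variable. Persistence separates patients who stopped from those who continued. Overall adherence needs at least 80% compliance and a second condition: "They have not dropped out of the study prior to the time of evaluation".

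Two secondary objectives in section 8.2 use these groups. One asks whether adherence is "associated with number of relapses at 12 (24) months". The other asks whether adherence to "treatment at 12 (24) months is associated with EDSS change at 12 (24) months". Section 9.1.2 lists both endpoints at fixed times. Relapses are recorded from visit to visit (section 9.2.7), so the count grows only while a patient is documented.

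**The concern.** The variable that defines the groups also decides how long their members are watched. Every patient classed persistent or adherent at 24 months has been followed for 24 months; every patient who stopped earlier has not. A relapse count at a nominal 24 months is then a 24-month count in one group and a shorter count in the other, and part of any difference is simply follow-up time.

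EDSS change raises a different problem. It does not accumulate with time as a count does. For a patient who stopped before month 12 or 24, the value at that visit does not exist, and the last EDSS comes from the discontinuation visit. This is missing data by design, with no fixed direction of bias.

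At stake are two named secondary objectives. A reader could take an artefact of follow-up length as evidence on how adherence relates to relapses.

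**Working it through.** **Plan's own figure.** The protocol gives no number for these comparisons. Its enrolment figure reproduces (200 / (1 − 0.20) = 250, section 9.5) but plays no part here.

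**Inputs.**
- Stopping by 24 months: 20% to 50%, taken as an assumed range. The ends are borrowed from the 20% missing-data allowance (section 9.5) and the roughly 50% two-year non-adherence cited in section 7.
- Relapse rate: 0.2 to 0.4 per year. This is an assumption; the protocol gives none.
- True relapse rate equal in all patients.

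**Step 1: truncation alone, stopping unrelated to relapse.** With exponential stopping and a proportion p stopped by 2 years, the hazard is h = −ln(1 − p)/2. Mean observed time among those stopped by time T (years) is 1/h − T·e^(−hT)/(1 − e^(−hT)).

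- T = 2, p = 0.20: 8.963 − 2 × 0.8/0.2 = 0.96 years, against 2.0.
- T = 2, p = 0.50: 2.885 − 2 × 0.5/0.5 = 0.89 years, against 2.0.
- T = 1: 0.49 years (p = 0.20) or 0.47 years (p = 0.50), against 1.0.

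The expected count is rate × observed time. At 0.4 per year and 24 months this is 0.38 or 0.35 in stoppers against 0.80 in persisters. The ratio does not depend on the rate. Across these cases truncation lowers the stoppers' count by 51% to 56%.

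**Step 2: effect on a test.** Assume 200 persisters, 50 stoppers with stop times uniform over 24 months, and equal true rates. The count ratio is about 0.50. A Poisson comparison without an offset gave p < 0.05 in roughly 49–56%, 76% and 95% of simulated studies at 0.2, 0.3 and 0.5 relapses per year (the first as a range over repeat simulations). With log(observed time) as offset it was 3–5%. The protocol does not specify the no-offset model; these figures show what an unadjusted count would do.

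**Step 3: relapses that trigger stopping.** Section 8.2 says relapses or EDSS changes may be reasons to end treatment. Simulation at 24 months, 0.4 relapses per year on average, between-patient (gamma) variation in rate with variance 0.5, and each relapse causing a stop with an assumed probability:

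| Background stopping | Trigger probability | Count, persistent | Count, non-persistent | Non-persistent if fully followed |
|---|---|---|---|---|
| 20% | 0 | 0.80 | 0.38 | 0.80 |
| 20% | 0.1 | 0.70 | 0.64 | 1.10 |
| 20% | 0.2 | 0.59 | 0.75 | 1.26 |
| 50% | 0.2 | 0.60 | 0.47 | 0.95 |

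Truncation always pulls the non-persistent count below its full-follow-up value, but the net comparison can go either way.

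**Step 4: what person-time repairs.** With no trigger, rates per person-year agree (0.40 against 0.40). With 50% background stopping and trigger 0.2 they are 0.30 in persistent and 0.54 in non-persistent patients. Full follow-up of the latter would give 0.954/2 = 0.48 per year. The on-treatment rate is therefore distorted upward in stoppers, and the offset is only a partial repair.

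**Step 5: who is affected.** A patient below 80% compliance who stays on Betaferon is not adherent but is fully documented. If half of a non-adherent group were such patients and half were stoppers observed for half the time, the count ratio would be (1.0 + 0.5)/2 = 0.75 rather than 0.50.

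**The case against.** The strongest objection concerns direction. A reader might infer that the plan makes stoppers look better. The documents do not support that: section 8.2 names relapse and EDSS change as possible causes of stopping, and step 3 shows the sign can reverse. This objection stands, and no net direction is claimed here.

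A second objection is that the protocol fixes no model for these objectives. The linear or logistic regression in section 9.7.5 is written for PTMS participation, and section 9.7.1 leaves statistical details to the SAP. An offset could well appear there, and nothing says the discontinuation-visit EDSS will be used as a 24-month value. This stands as far as modelling goes. But the fixed-time count and the rule ending documentation are protocol text, and no SAP can recover relapses or EDSS values that were never collected. Section 11.2 extends adverse event reporting to 30 days after the last dose; it does not extend the relapse count or EDSS.

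Third, section 8.2 may intend relapse and EDSS as influences on adherence, in which case data before the stop are the relevant ones. That is a legitimate question, but a count over unequal exposure needs person-time there too.

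Fourth, the analyses are exploratory, and section 9.7.7 warns of loss to follow-up and urges extreme caution over post-baseline variables. It does not mention that observation time differs by construction between the compared groups, and a call for caution does not correct the comparison.

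**Conclusion.** The point holds in a limited form. For persistence, and for the persistence part of overall adherence, observation time differs by construction. If true rates are equal and stopping is unrelated to relapse, stoppers' relapse counts are about half those of persisters (51–56% lower when 20–50% stop by 24 months). This size rests on the assumed stopping pattern; the mechanism does not. The net direction in the real data is unknown.

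EDSS change at 12 or 24 months is not observed in patients who stopped before that visit, so its association with persistence cannot be estimated from the planned data.

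Two further inferences should be resisted. One is that an offset cures the relapse comparison: it leaves bias from relapse-driven stopping in place. The other is that every adherence analysis is compromised: patients with low compliance who remain on Betaferon are documented throughout. The change should be made, but it concerns secondary objectives only.

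**What to change.** 1. **Relapses.** Define the endpoint as a rate over documented time, analysed by Poisson or negative binomial regression with log(observed time) as offset. State that this removes the unequal-follow-up artefact but not bias from relapse-driven stopping, so the result for stoppers is an on-treatment association only.
2. **EDSS.** Restrict the 12/24-month objective to compliance (%) in patients with an EDSS at that visit. Do not use the discontinuation-visit EDSS as a 12- or 24-month value. State that the association of persistence with 12/24-month EDSS change is not estimable.

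The cost is wording in the objectives and the SAP. Visit dates, relapse onset dates and the last injection date are already on the case report form. The downside is narrower relapse and EDSS claims. Broader claims would need relapse and EDSS documentation to continue after treatment stops, which is a larger change to the design.

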#### 9.2.5 Replacement

Patients will not be replaced after drop out.

#### 9.2.6 Representativeness

No further selection than outlined in Sections 9.2.1 - 9.2.3 should be made and patients should be enrolled consecutively in order to avoid selection bias. With respect to site selection this study could have potential limited representativeness (convenience sample) as we are looking for experienced specialized sites & departments in the management and treatment of MS.

# 9.2.7 Visits

The investigator documents an initial visit, follow-up visits and a final visit for each patient in the case report form (CRF). Follow-up visits occur during routine practice, the study protocol does not define exact referral dates for those visits. However, documented visits should be approximately six months apart. The final visit is to be documented after approximately 24 months. The observation period for each patient is therefore approximately 24 months.

# Enrollment / Initial visit

Once a patient is found eligible for inclusion, the investigator will inform the patient about the study. Where applicable, this will include discussing the consent form and asking the patient to read and - when agreeing to participate - sign the informed consent.

Typical information to be collected at the baseline visit includes:

- Date of visit
- Date of birth (at least year)
- Sex (female, male)
- Race / ethnicity (Caucasian, asian, black, other)
- Height (cm)
- Weight (kg)
- Smoking (current, past, never)
- Employment status (employed, retired, keeping house, student, seeking work, self-employed, other, not reported)
- Education level (elementary education, secondary education, college or university education, not reported)
- Marital status (married/partnership, single)
- Medical history
  - Concomitant diseases
  - Concomitant medication
    - Trade name or INN
    - Start date (at least year)
    - Stop date or "continued"
    - Daily dose, if applicable
    - Indication
- Intake of vitamin D supplements (yes vs. no; if yes which dosage?)
- Intake of other nutrients or vitamins (yes vs. no)

IMPACT number 18016; BETAPREDICT; Version 1.0, 12 February 2015

- Specific MS history
  - Date of first clinical event suggestive of MS (DD/MM/YYYY)
  - Date of initial diagnosis (DD/MM/YYY)
  - diagnostic criteria
    - o according to McDonald criteria
    - o according to Poser criteria (CDMS)
  - Number of further demyelinating events/relapses (number during past 2 years)
    - If number >0: date of onset (DD/MM/YYYY), ongoing
  - Concomitant diseases of special interest
    - Depression
    - o Anxiety
    - o Fatigue
  - Betaferon® administration record
    - Betaferon® treatment (ongoing/naive)
    - Date of first Betaferon® injection (DD/MM/YYYY)
  - Current application form for Betaferon® (prior to study)
    - Manual injection (yes/no)
    - Use of auto-injection device (yes/no)
      - If Yes, please tick (BETACONNECTTM, BETACOMFORT®, BETAJECT Comfort®, BETAJECT lite®, other)
  - Treatment days with Betaferon® during last month
    - Number of expected treatment days
    - Number of true treatment days
    - o N/A
  - Participation in the BETAPLUS® nurse support program (yes/no)
  - Participation in the PTMS program (yes/no)
  - injection-site reactions (yes vs. no; if yes: redness, other discoloration, hematoma, induration, lipodystrophy, necrosis; if yes: mild, moderate, severe)
  - previous use of other MS drugs (yes/no; if yes please specify)
- Examination results
  - EDSS

- Local skin reactions (yes/no)
  - If yes; please tick

a) (redness, other discoloration, hematoma, induration, lipodystrophy/-

atrophy, necrosis)

b) (mild, moderate, severe)

- Patient Questionnaire (QQ) results available (yes/no), if yes
  - please send back
- SF-36 results available (yes/no), if yes
  - please send back
- EQ-5D results available (yes/no), if yes
  - please send back
- CES-D results available (yes/no), if yes
  - please send back
- WEIMuS results available (yes/no), if yes
  - please send back
- SDMT results available (yes/no), if yes
  - please send back
- CMSS results available (yes/no)\*, if yes
  - please send back
- MSSM-R results available (yes/no), if yes
  - please send back
- ISU-DYA results available (yes/no)\*, if yes
  - please send back

\*only for patients participating in the PTMS program.

